7.4. Guidelines for Ibrutinib and Venetoclax Management with Surgeries or Procedure

Ibrutinib may increase risk of bleeding with invasive procedures or surgery. The following guidance should be applied to the use of ibrutinib in the perioperative period for subjects who require surgical intervention or an invasive procedure while receiving ibrutinib:

- **Minor Surgical Procedures**

For minor procedures (such as a central line placement, skin or needle biopsy, lumbar puncture [other than shunt reservoir access], thoracentesis, or paracentesis) ibrutinib should be held for at least 3 days prior to the procedure and should not be restarted for at least 3 days after the procedure. For bone marrow biopsies that are performed while the subject is on ibrutinib, it is not necessary to hold ibrutinib for these procedures. Venetoclax can be continued as per physician discretion for planned or emergency procedures.

- **Major Surgical Procedures**

For any surgery or invasive procedure requiring sutures or staples for closure, ibrutinib should be held at least 7 days prior to the intervention (except for emergency procedures) and should be held at least 7 days after the procedure and restarted at the discretion of the investigator when the surgical site is reasonably healed without serosanguinous drainage or the need for drainage tubes. Venetoclax can be continued as per physician discretion for planned or emergency procedures.

8. DEFINITION OF DOSE LIMITING TOXICITY

Assessment of DLT will be defined as any non-hematologic or hematologic toxicity listed below that occurs during the first cycle of treatment. Toxicities will be graded according to the National Cancer Institute Common Terminology Criteria for Adverse Events (NCI CTCAE), version 4.03. Patients will be included in the DLT assessment as long as they have received at least 85% of planned doses of each drug or have experienced a DLT any time after the 1st dose. For each patient who did not receive $\geq 85\%$ of therapy, another patient will be enrolled at that dose level.

8.1. Non-hematologic toxicity

Non-hematologic toxicity will be defined as any of the following:

- Any Grade 3 or 4 non-hematologic toxicity except
 - Grade 3 fever without neutropenia
 - Grade 3 fatigue
 - Anorexia
 - Grade 3 nausea, vomiting or diarrhea not requiring tube feeding, total parenteral nutrition, or requiring prolonged hospitalization
- Failure of any Grade 3 or 4 fever without neutropenia, fatigue, anorexia, nausea, vomiting, or diarrhea to resolve or recover to baseline level after delaying the next dose by more than 2 weeks
- Any treatment-related death

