5.2. Treatment Plan

5.2.1 Phase I Study Treatment Plan

Patients will be treated with combination therapy of ibrutinib and venetoclax according to their assigned dose level cohort. Dose escalation is described in Table 2 and the paragraph below.

Each cycle is 28-days. Patients will be monitored for dose limiting toxicity (DLT) weekly during Cycle 1. Patients will receive the combination until progression or unacceptable toxicity. Patients will be followed during therapy through progression until next line of therapy. Questions regarding treatment should be directed to the Study Chair.

Table 2: Dose Level Cohorts

Dose Levels		
Dose Level	Ibrutinib	Venetoclax
0	420 mg	400 mg
1	560 mg	400 mg
2	560 mg	600 mg

*Dose Level 0 is the starting level dose

The MTD finding procedure starts at DL0. Three patients will initially be entered at this dose level.

- If 0/3 DLT is observed, dose escalation will continue to the next upper dose level.
- If $\geq 2/3$ DLTs are observed, then the dose finding procedure will be terminated.
- If 1/3 DLT is observed, then 3 additional patients will be enrolled in the same dose level. If no DLT is observed from the additional 3 patients, then dose escalation will continue to the next upper dose level. If any DLT is observed from the 3 additional patients, then the

previously lower dose will be chosen as the MTD and the dose finding procedure will be terminated.

Dose escalation will be continued as per Table 2 until a dose with no more than 1/6 DLTs is found and is chosen as the MTD. Once the MTD is determined, there will be a 17-patient phase II study at this dose level.

The original design of this study included a Dose Level 3 of Ibrutinib 560 mg and Venetoclax 800 mg. After examining the pharmacokinetic data at Dose Level 2, which showed a significantly increased systemic plasma exposure to ibrutinib, it was determined not to proceed with Dose Level 3. One patient had initiated therapy at Dose Level 3 before the decision was made for closure.

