12.1. Phase I study

The maximum tolerated dose (MTD) finding procedure uses the traditional 3+3 cohort method, starting from dose level 0. A dose level will be chosen as the MTD if it has 6 patients, and number of observed DLT is 0 or 1. The MTD is also known as the recommended phase II dose.

Three patients will be enrolled at Dose Level 0 (DL0). Patients will be assessed for DLTs during Cycle 1.

Three patients will initially be entered at DL0.

- If 0/3 DLT is observed, dose escalation will continue to the next upper dose level.
- If $\geq 2/3$ DLTs are observed, then the dose finding procedure will be terminated.
- If 1/3 DLT is observed, then 3 additional patients will be enrolled in the same dose level.

If no DLT is observed from the additional 3 patients, then dose escalation will continue to

the next upper dose level. If any DLT is observed from the 3 additional patients, then the previously lower dose will be chosen as the MTD and the dose finding procedure will be terminated.

Dose escalation will be continued as per Table 2 until a dose with no more than 1/6 DLTs is found and is chosen as the MTD.

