12.3. Toxicity Evaluation

Ineligible patients will be replaced by new eligible patients during both phases of the study and will be excluded in the data analysis. Ineligible patients are defined as patients who were initially believed to be eligible, but with full screening have been found to be ineligible.

Toxicity (attribute and grade) will be summarized for each dose level as per the NCI Common

Terminology Criteria for Adverse Events (CTCAE Version 4.03) for all patients who receive at least one dose of study treatment.

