12.4. Target Accrual and Study Duration

The real sample size of this study is variable. The minimum required sample size is 6, but this number may change based on the number of DLTs experienced by patients during the phase I portion of the study. The maximum samples size will be 35 patients (= 3 dose levels x 6 patients + 17 patients for expansion). The patient accrual will be closed as soon as the MTD is found and the phase II expansion is completed. We will have conference calls every 2 weeks with all sites with patients enrolled to discuss toxicity in individual cases. The safety data of all patients will be reviewed during the biweekly conference calls, and the stopping rule for the 3+3 cohort scheme will be applied.

The estimated accrual rate is about 2 patients per month. As a result, it will take about 13 months to find and expand the MTD. However, observation of PFS will require longer follow-up. A maximum of 10 years of follow-up is required for all patients. Once the targeted number of patients has been accrued to this study, a notice suspending accrual will be issued to the Group via email broadcast announcing permanent termination of patient accrual within 14 days.

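### In the Section 8.1 DLT exceptions anorexia has no grade limit, so Grade 4 anorexia is not a DLT at onset; the gastrointestinal exception beside it is ambiguously worded

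*Combined protocol and SAP*

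**What the plan says.** Section 8 defines a DLT as "any non-hematologic or hematologic toxicity listed below that occurs during the first cycle of treatment". Section 5.2.1 sets the cycle at 28 days.

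Section 8.1 counts any Grade 3 or 4 non-hematologic toxicity, with four exceptions:

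- fever without neutropenia, limited to Grade 3;
- fatigue, limited to Grade 3;
- anorexia, with no grade stated;
- "Grade 3 nausea, vomiting or diarrhea not requiring tube feeding, total parenteral nutrition, or requiring prolonged hospitalization".

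Two further bullets bring events back in. One covers any treatment-related death. The other covers "Failure of any Grade 3 or 4 fever without neutropenia, fatigue, anorexia, nausea, vomiting, or diarrhea to resolve or recover to baseline level" once the next dose has been delayed by more than 2 weeks.

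The counts feed the 3+3 rule. Section 12.1 states: "A dose level will be chosen as the MTD if it has 6 patients, and number of observed DLT is 0 or 1". It also equates the MTD with the recommended phase II dose. Section 5.2.1 reports that a former Dose Level 3 was closed after pharmacokinetic data from Dose Level 2 had been examined, and adds: "One patient had initiated therapy at Dose Level 3 before the decision was made for closure".

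**The concern.** A DLT definition is a decision rule, and sites at three centers apply it. Two phrases in this one do not do what they probably should.

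The first is the missing grade on anorexia. A reader who follows the text does not count Grade 4 anorexia when it occurs, while Grade 4 fever, fatigue, nausea, vomiting and diarrhea all count at onset.

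The second is the repeated *requiring* in the gastrointestinal exception. It lets a reader attach *not* to the feeding items only, and so treat prolonged hospitalization as a reason to exempt a Grade 3 event.

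In either case an event that most clinicians would want counted could be left out of a cohort's DLT total. At stake are the escalation decision at that level and the choice of MTD.

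**Working it through.** The plan gives no figure to reproduce here. The check compares the relevant texts and then does short arithmetic on the consequences.

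**1. Is a grade limit for anorexia supplied elsewhere?** The other DLT text is in Sections 5.2.1, 8, 8.2 and 12.1. None of it grades anorexia. Section 6.2 lists toxicities that trigger dose modification, but it does not define DLTs.

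**2. Does the non-resolution bullet show that the exemption is deliberate?** No. It names Grade 3 or 4 for every event in its list, including fatigue, nausea, vomiting and diarrhea, whose Grade 4 forms are already DLTs at onset. An omitted *Grade 3* is the likelier explanation.

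**3. How much does the non-resolution bullet recover?** Suppose the first held dose falls on Day d. The delay exceeds 14 days once the Day d + 14 dose is also missed. If the failure to resolve must itself fall within Cycle 1, then d + 14 ≤ 28, so d ≤ 14. Anorexia that first stops dosing after Day 14 could not qualify in time. Section 8 does not say whether the failure must fall within the cycle, so this limit is conditional.

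**4. How can the gastrointestinal exception be read?**

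| Reading | Grade 3, tube feeding or parenteral nutrition needed | Grade 3, prolonged hospitalization needed | Grade 4 |
|---|---|---|---|
| *Not* governs all three items (probable intent) | DLT | DLT | DLT |
| *Not* governs the feeding items only | DLT | exempt at onset | DLT |

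The readings differ in one cell.

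**5. How many patients would need a re-read?** Because a patient started Dose Level 3, Dose Levels 0, 1 and 2 had each been passed. Under the 3+3 rule each took 3 to 6 counted patients, in line with the accrual formula in Section 12.4 ("3 dose levels x 6 patients + 17 patients for expansion").

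- Minimum: 3 + 3 + 3 + 1 = 10
- Maximum: 6 + 6 + 6 + 1 = 19
- Plus anyone replaced under the 85% rule in Section 8

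**6. What does one added DLT do at a level?**

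| Count as recorded | Count with one more DLT | Effect |
|---|---|---|
| 0/3 | 1/3 | three more patients needed before escalating |
| 0/6 | 1/6 | still meets the MTD rule (0 or 1) |
| 1/6 | 2/6 | no longer meets the MTD rule |

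No probability is attached. The documents give no Cycle 1 rate for Grade 4 anorexia, or for Grade 3 gastrointestinal events with prolonged hospitalization, on this combination.

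**The case against.** The case for leaving this alone has real force.

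**The gastrointestinal wording has a natural reading.** One can take *not* as covering the whole series and the second *requiring* as redundant. The rival reading gives an odd rule, in which tube feeding makes an event a DLT and prolonged hospitalization excuses it. This stands. A reader might infer that the protocol means to exempt hospitalized patients, and the documents do not support that. The point here is ambiguity only.

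**The anorexia gap is narrow.** A Grade 3 or 4 non-hematologic toxicity outside the exceptions that accompanies anorexia is a DLT in its own right, and treatment-related death always counts. This stands too. The gap is Grade 4 anorexia with no other qualifying toxicity that does not meet the non-resolution bullet.

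**Patients remain protected.** Section 6.2 and Table 4 withhold both drugs for Grade 3 or higher non-hematologic toxicity, with no exception for anorexia. Section 13.1.2 makes life-threatening events, and hospitalization beyond 24 hours or prolonged, serious adverse events. Section 14.7 sends those to the IRB, which may suspend accrual, and has the DSMC review toxicity every 4 months. DLT monitoring is weekly in Cycle 1 (Section 5.2.1), calls are held every 2 weeks (Section 12.4), and Section 12.3 summarizes toxicity "for all patients who receive at least one dose of study treatment". These keep events visible and managed. None states a different DLT definition, so none corrects a cohort count.

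**Severity should not be borrowed.** It is tempting to call the uncounted event life-threatening by citing the grading scale in Section 13.1.3. That scale applies only to events not listed in CTCAE, whereas Section 8 grades DLTs by CTCAE version 4.03. The point does not need the label.

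**The issue is mostly retrospective.** Dose Level 3 had opened and closed, so escalation is largely finished. This stands, with one qualification: if Dose Level 2 was passed on 0/3, Section 12.1 requires three more patients there before it can be the MTD, and the definition would apply to them.

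**Conclusion.** The point holds, with low consequence. As written, Section 8.1 does not count Grade 4 anorexia as a DLT at onset, and nothing else in the DLT text closes that gap. The gastrointestinal exception is ambiguous, with the safer reading the probable one.

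The effect is confined to cohort DLT counts and the MTD. For one reclassified event to disqualify a level as MTD, that level must already have 1 DLT; at 0/3 it would have called for three more patients before escalation.

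A reader might infer that a DLT was missed, or that the phase II dose is wrong. The documents do not support either: they report no disputed event, and they attribute the closure of Dose Level 3 to ibrutinib exposure.

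The conclusion rests on two assumptions. One is that sites apply Section 8.1 as printed. The other is that Dose Levels 0 to 2 were passed under the stated 3+3 rule, which gives the range of 10 to 19 patients.

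**What to change.** 1. In Section 8.1, change the anorexia exception to *Grade 3 anorexia*.
2. In the gastrointestinal exception, delete the second *requiring*, so that one *not requiring* governs tube feeding, parenteral nutrition and prolonged hospitalization alike. The sponsor's clinicians should confirm that this is the intent.
3. Re-read Cycle 1 anorexia, nausea, vomiting and diarrhea in all phase I patients against the corrected text, and state whether any cohort's DLT count changes.
4. Include replaced patients. Section 8 says that for each patient below 85% of therapy "another patient will be enrolled at that dose level", so someone with an uncounted event could have left the denominator. Whether that can happen depends on whether planned doses include doses held under the protocol. It is a separate matter, which the wording change does not settle.

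The cost is a few words in an amendment and a review of 10 to 19 patients' Cycle 1 events, plus any replaced. The downside is that a cohort's DLT count could rise, and a level at 1/6 would then no longer meet the MTD rule.

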8.2. Hematologic Toxicity

All subjects, regardless of baseline hematologic status (i.e. neutrophil and platelet counts), will be included in the DLT assessment. Hematologic toxicity will be defined as any of the following:

- Any Grade 4 hematologic toxicity, except for Grade 4 neutropenia ≤ 5 days
- Grade 4 neutropenia > 5 days
- Grade 3 or 4 neutropenia complicated by fever $\geq 38.5^{\circ}\text{C}$ or infection
- Grade 4 thrombocytopenia (must be repeated same day by a separate peripheral blood draw to confirm toxicity), that is considered a treatment emergent adverse event
- Grade 3 thrombocytopenia with clinically significant bleeding
- Grade 2 thrombocytopenia with clinically significant bleeding felt to be drug related
- Grade 4 anemia unexplained by underlying disease

9. DRUG FORMULATION, AVAILABILITY, AND PREPARATION

9.1. Ibrutinib

Availability

Ibrutinib is supplied as hard gelatin capsules containing micronized ibrutinib and the following excipients: microcrystalline cellulose, croscarmellose sodium, sodium lauryl sulfate, and may contain magnesium stearate. Capsules are available 140 mg strength size 0, gray, hard gelatin capsule. Capsules are packaged in high-density polyethylene (HDPE) bottles with an induction seal and a child resistant screw top cap. Each bottle contains 120 capsules.

Storage and Stability

Ibrutinib Hard Gelatin Capsules should be stored at $15 - 25^{\circ}\text{C}$. Shelf life surveillance of the intact bottles is ongoing.

Administration

Ibrutinib is taken orally, around the same time each day with 8 ounces (approximately 240 mL) of water. The capsules should be swallowed intact.

The capsules should be swallowed intact and subjects should not attempt to open capsules or dissolve them in water. The use of strong CYP3A inhibitors/inducers, and grapefruit and Seville oranges should be avoided for the duration of the study (see Appendix V).

If a dose is not taken at the scheduled time, it can be taken as soon as possible on the same day with a return to the normal schedule the following day. The subject should not take extra capsules to make up the missed dose.

9.2. Venetoclax

Availability

The venetoclax tablets will be packaged in high-density polyethylene (HDPE) plastic bottles or blister packs to accommodate the study design. Each container will be labeled per local

regulatory requirements. Venetoclax is available in tablets of 100 mg consisting of light yellow to dark yellow powder.

Storage and Stability

The clinical supply should be stored at 15° to 25°C (59° to 77°F).

Administration

The tablets are to be taken around the same time each day with 8 ounces (approximately 240 mL) of water. The tablets should be swallowed intact and subjects should not attempt to open tablets or dissolve them in water. All subjects will be trained to self-administer venetoclax orally QD 30 minutes after the completion of breakfast or the subject's first meal of the day.

Refer to the pharmacy manual/site investigational product manual for additional guidance on study drug storage, preparation and handling.

10. CORRELATIVE SCIENCE COMPANION STUDY

10.1. Next-Generation Sequencing

Next generation sequencing via the MI TumorSeek™ will be performed on bone marrow aspirate samples from eligible patients, prior to initiation of targeted therapy. MI TumorSeek™ is a 596 gene Next-Generation Sequencing Cancer Service available through Caris Life Sciences. Patients will undergo a bone marrow core biopsy and aspirate prior to initiation of therapy. One 1-cm core biopsy will be submitted to Caris Life Sciences in 50 mL of 10 % neutral buffered formalin overnight. If the patient is found to have greater than 20% involvement with FL in their bone marrow sample by standard hematopathology review, MI TumorSeek™ analysis will be performed on the submitted sample through Caris Life Sciences. If the patient lacks greater than 20% lymphomatous involvement of their bone marrow, they will be recommended to undergo a biopsy of an affected lymph node or other disease-involved area as determined by pretreatment staging PET-CT. The MI TumorSeek™ assay will be repeated on new tissue samples from patients who initially achieve a partial or complete remission and subsequently progress. Special focus will be placed on BTK and BCL-2, including variants of unknown significance, as well as PI3K, as idelalisib is an FDA approved PI3Kδ inhibitor the patient may have received previously or will subsequently receive.

10.2. BCL-2 Family Proteins

Levels of expression of various BCL-2 family member proteins will be assessed on tumor samples from patients prior to treatment, on bone marrow biopsy samples after achieving a complete response, and tumor samples at progression. Assessments will be performed on bone marrow biopsy core samples of patients with lymphomatous involvement. One centimeter of the core biopsy will be submitted to the Lombardi Comprehensive Cancer Center

Histopathology and Tissue Shared Resource (HTSR) for processing. The presence of tumor will be assessed by H&E. Sections will be stained by the HTSR for BCL-2 family proteins including BCL-2, MCL-1, BIM, and BCL-XL. The stained slides will be subsequently transported to the Department of Pathology for H-score assessment of individual BCL-2 family member proteins. Samples will be reviewed independently by two hematopathologists ([name]; [name]). If the bone marrow is not involved, the patient may be recommended to undergo a biopsy of an affected lymph node or other disease-involved area as determined by pretreatment staging PET-CT. Alternatively, if tissue is already available from a recent biopsy of an affected area, it may be submitted. These patients will only undergo a follow up biopsy if they experience a progression on study.

10.3. Tumor Cell Cultures

The cell culture studies will be conducted in the laboratory of [name], who has recently established similar primary co-culture models with other B-cell malignancies. Bone marrow aspirates will be assessed for tumor cell content as described above and processed by ficoll-gradient centrifugation. Five milliliters of aspirate will be collected in a yellow citrate tube. Depending on tumor cell percentage, the cells may be enriched by depletion of CD3, CD14, and CD16 positive cells with magnetic beads or used directly after assessment of viability and cell number. A variety of co-culture systems will be tested initially including culture with the follicular dendritic cell-like cell line HK, the immortalized mesenchymal stromal cell line HS-5, and primary bone marrow-derived mesenchymal stromal cells. [28-30] The tumor cells will be plated in IDEM, or α -MEM supplemented with 10%FBS on monolayers of un-modified or irradiated co-culture cells plated in wells. Tumor cell viability and proliferation will be assessed at various periods after culture by EdU-Click-IT-Alexa Fluor labeling assay and colorimetric vital dye assay. Drug sensitivity assays will be done in a similar fashion by treating wells of co-cultured cells with various concentrations of venetoclax and ibrutinib alone and in combination for 24 hours followed by staining the cells with CD19 to mark the tumor cells and Calcein AM to assess viability, followed by quantification using a custom MetaMorph macro.

11. SUBJECT COMPLETION AND WITHDRAWAL

11.1. Completion

The investigator will conduct the study in compliance with the protocol and complete the study within the timeframe specified in the contract. Continuation of this study beyond this date must be mutually agreed upon in writing by both the investigator and the sponsor. The investigator will provide a final report to the IEC/IRB following conclusion of the study. The investigator must retain any records related to the study according to local requirements. The end-of-study is defined as the date of the last subject's last visit.

